6.2.3 Day 8 (\pm 2 days)

The following evaluations will be performed at Day 8 (\pm 2 days):

- Vital signs
- Serum HGF
- Injection site reaction assessment
- Analgesic use
- Concomitant medications
- Adverse events

6.2.4 Day 15 (± 3 days) Second Study Dose Administration

The second dose of study drug will be administered at Day 15 (\pm 3 days). Prior to the administration of the study agent, the following will be performed:

- Physical exam
- Vital signs (immediately after study drug administration and at 15, 30, and 60 minutes post-dose)
- Photograph and measurement of ulcer
- Urine Pregnancy test (females of childbearing potential)
- Clinical laboratory tests
- Tumor markers
- Serum HGF level

- anti-HGF antibodies
- TcPO₂
- Hemodynamic assessment
- Pain VAS
- Analgesic use
- Concomitant medications
- Adverse events

The study drug will be administered in the same manner and in the same dose as performed on Day 1. Following study drug administration, the following evaluations will be performed:

- Vital signs
- Injection site reaction assessment
- Endothelial progenitor cell assay
- Adverse events
- 6.2.5 Day 16 (post 2nd dosing)

The following procedures will be performed at the Day 16 visit:

- Vital signs
- Adverse events
- Clinical laboratory tests
- Analgesic use
- Injection site reaction assessment
- Concomitant medications
- 6.2.6 Day 21 (\pm 3 days)

The following procedures will be performed at the Day 21 (+ 3 days) visit

- Vital signs
- Serum HGF
- VM202 DNA levels
- Injection site reaction assessment
- Analgesic use
- Concomitant medications
- Adverse events
- 6.2.7 Day 28 (\pm 3 days)

The following evaluations will be performed at Day 28 (\pm 3 days):

- Physical exam
- Vital signs
- Photograph and measurement of ulcer
- Clinical laboratory tests
- Hemodynamic assessments (ABI, TBI, Wave Form)
- Pain VAS
- TcPO₂
- Endothelial progenitor cell assay
- Analgesic use
- Injection site reaction assessment
- Concomitant medications
- Adverse events

After all subjects in Cohort I have completed the Day 28 visit, enrollment will be temporarily suspended until the DSMC has reviewed all of the safety data for all subjects. If the DSMC recommends that the trial continue, enrollment in Cohort II will commence and all of the procedures from Day -30 through Day 28 will be repeated for Cohort II.

After all subjects in Cohort II have completed the Day 28 visit, enrollment will be temporarily suspended until the DSMC has reviewed all of the safety data for all subjects. If the DSMC recommends that the trial continue, enrollment in Cohort III will commence and all of the procedures from Day -30 through Day 28 will be repeated for Cohort III.

After the first subjects in Cohort III have completed the Day 28 visit and subsequent to the dosing of the other subjects in the same cohort, enrollment will be temporarily suspended until the DSMC has reviewed all of the safety data for all subjects. If the DSMC recommends that the trial continue, enrollment in Cohort IV will commence and all of the procedures from Day -30 through Day 28 will be repeated for Cohort IV.

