Subjects selected for this study will all have critical limb ischemia defined as partial or complete obstruction of a major artery perfusing either the upper or lower extremity that results in pain either at rest or with exertion, numbness, coldness and/or skin ulceration. They may also be a history of prior amputation, dry gangrene or atrophy associated with the above symptoms. Subjects will not be a candidate for either surgical revascularization or angioplasty.

Number of Study Subjects

There will 12-15 subjects selected for participation in this study with 3 subjects treated in each of four (4) study cohorts. There will be an additional 3 patients treated in a cohort if 1/3 subjects experiences a DLT and if the DSMC recommends continuing the trial.

Schedule of Assessments

The schedule of assessments is listed below in Table 4-1.

Table 4-1 Study Procedures Chart	Screen / Baseline		Treatment Period												
		Firs	First Dose Follow-Up Second Dose 2 nd Follow-Up ⁵												
	Day -30 to Day 1	Day 1 pre-dose	Day 1 post-dose	Day 8 (+/- 2days)	Day 15 Pre dose (+/- 3 days)	Day15 Post-dose	Day 16	Day 21 (+/- 3 days)	Day 28 (+/- 3 days)	Day 59 (+/- 7 days)	Day 91 (+/- 7 days)	Day 180 (+/- 10 days)	Day 365 (+/- 10 days)	Unscheduled Visit	Early Termination
Consent Form	X														
Confirm Eligibility		X													
Medical History	X														
Chest X-ray or CT scan of chest ¹	X												X		X
Physical Exam	X				X				X	X	X	X	X	X	X
Vital Signs (HR, BP, Respiratory)	X	X	X	X	X	X	X	X	X	X	X	X	X	X	X
Retinal Fundoscopy	X												X		X
Pregnancy Test	X				X 6										
Photograph and measurement of ulcer	X	X			X				X	X	X	X	X		X
Clinical Lab Tests	X	X			X		X		X	X	X	X	X	X	X
Tumor markers ²	X				X					X		X	X		
Infection tests ³	X									X		X	X		X
Serum HGF		X		X	X			X		X					
anti-HGF antibodies		X			X					X		X		X	X
Blood VM202 DNA		X						X		X^7					
12-lead ECG	X														
High Resolution MRA	X										X	X			X
Hemodynamic Assessment (ABI, TBI,	X	X			X				X	X	X	X	X	X	X
Wave Form)	Λ	Λ			Λ				Λ	Λ	Λ	Λ	Λ	Λ	Λ
Pain VAS	X	X			X				X	X	X	X	X	X	X
Subject Analgesic use	X	X		X	X		X	X	X	X	X	X	X	X	
TcPO ₂	X	X			X				X	X	X	X	X	X	X
Injection site reaction assessment			X	X		X	X	X	X	X					
Mammogram ⁴	X														
Endothelial Progenitor Cell Assay	X		X			X			X	X		X	X	X	X
Concomitant Medications	X	X		X	X		X	X	X	X	X	X	X	X	X
Adverse Events		X	X	X	X	X	X	X	X	X	X	X	X	X	X

CT scan of the chest instead of chest X-ray will be performed if previous tobacco use

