- Review all prior evaluations and confirm that subject meets all entry criteria
- Vital signs
- Digital photography and measurement of ulcer (if present)
- Clinical laboratory tests (chemistry, hematology, and urinalysis)
- Serum HGF
- Anti-HGF antibody level
- VM202 DNA level
- Hemodynamic assessments (ABI, TBI, Wave Form)
- TcPO₂
- Pain VAS
- Analgesic use
- Concomitant medications
- Adverse Events

If the subject meets all eligibility criteria, the following will be performed:

- Obtain study drug from the pharmacy
- Administer study drug in 8 separate injections as described above

After study drug administration, the subject will remain in a comfortable, supine position for observation for at least 60 minutes prior to being discharged. Any adverse reaction occurring during this period will be documented on the CRF.

Following study drug administration, the following evaluations will be performed:

- Vital signs (immediately after study drug administration and at 15, 30, and 60 minutes post-dose)
- Endothelial progenitor cell assay
- Concomitant medications
- Injection site reaction assessment

Adverse events

The subject is instructed to call the Study Coordinator if any of the following occur after discharge from the clinic:

- Hives
- Fever
- Rash
- Difficulty breathing
- Itching
- Worsening of a leg ulcer
- Redness or flushing at the site of the test dose

If any of the above occurs, the subject will be instructed to call the clinic immediately and seek medical attention either at the clinic or to go to the nearest Emergency Room for immediate treatment and evaluation. No further study drug administration will occur until it is determined if this is a DLT or as directed by the treating physician.

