7.1.2 Physical Examination

The Investigator will perform a full physical examination at Baseline and at Days 15, 28, 59, 91, 180 and 365. All changes from the Baseline will be documented on the CRF pages at the time of the follow-up physical examination.

7 1 2 1 Assessment of CLI

The lower extremities will be examined specifically for clinical evidence of CLI, such as ischemic rest pain, ischemic ulceration, gangrenous skin changes, or residual open wound(s) from minor amputation.

Subjects will be classified as having ischemic rest pain if the pain required analysis for more than 2 weeks, and includes the following clinical characteristics:

- 1. Persistent or recurrent pain of the distal portion of the leg (usually toes, forefoot or ankle),
- 2. Pain begins or is increased, on elevation of the leg and improved by dependency.

Ischemic ulceration and gangrenous skin changes are equivalent necrotizing processes for the purpose of this study. In the case of residual open wound(s) from minor amputation, these will be considered ulceration(s) for the purposes of this assessment.

The Investigator will assess the number of individual ulcers and/or gangrenous tissue site(s) for location and size. Excess necrotic tissue and eschar will be removed when possible before taking measurements. Photographs of each ulceration/gangrene area will be taken for documentation purposes only. Two photographs of each ulceration/gangrene area will be obtained at each efficacy time point regardless of whether the area still contains the ulcer/gangrene, and regardless of how many doses of test material the subject received. During the monitoring visit, the monitor will retrieve one of the two photographs for each ulceration/gangrene area. The border of all photographs will be labeled with the photograph date, subject's initials, and the subject's study number assignment.

On efficacy assessment visits, the ulceration/gangrene area will be considered completely healed if assessed as having complete skin closure without drainage or dressing requirements. An ulceration/gangrene area that heals but re-appears and is unhealed at the assessment will be considered not healed. If the subject is discontinued from treatment, he/she will continue to be followed for ulceration/gangrene evaluations so that the subject's data can be included in analyses. If the subject is lost to follow-up without a proper ulceration/gangrene evaluation, the subject will be considered not to have healed.

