7.1.6 Local Injection Site Reaction Assessment

Local injection sites reactions will be assessed using the grading defined by the National Cancer Institute's Common Terminology for Adverse Events v3.0. The grading categories are as follows and will be recorded on the CRF:

Adverse Event	Grade 1	Grade 2	Grade 3	Grade 4	Grade 5
Injection site reaction	Pain; itching; erythema	Pain or swelling, with inflammation or phlebitis	Ulceration or necrosis that is severe; operative intervention indicated		
Ulceration		Superficial ulceration <2 cm size; local wound care; medical intervention indicated	Ulceration ≥2 cm size; operative debridement, primary closure or other invasive intervention indicated (e.g. hyperbaric oxygen)	Life- threatening consequences; major invasive intervention indicated (e.g., complete resection, tissue reconstruction, flap, or grafting	Death
Allergic reaction/ hypersensitivity	Transient flushing or rash; drug fever <38°C (<100.4°F)	Rash; flushing; urticaria; dyspnea; drug fever ≥38°C (≥100.4°F	Symptomatic bronchospasm, with or without urticaria; parenteral medications(s) indicated; allergy-related edema/ angioedema; hypotension	Anaphylaxis	Death

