7.1.9 Dose Limiting Toxicity (DLT)

Dose limiting toxicity will be defined as the occurrence of any of the following:

- Acute anaphylaxis including erythema, hives, wheals, wheezing, stridor or respiratory distress
- Temperature >102°F with negative blood cultures within 24 hours of study drug administration
- Evidence for active tissue necrosis at the injection site within two weeks of study drug administration

Dose limiting toxicities will be recorded on the CRF. In the event of a DLT at any dose, 3 additional subjects will be added to the dose cohort in which the toxicity was observed. If no additional DLTs are observed in the 6 subjects in this dose level, it will be considered the Maximum Tolerated Dose (MTD). If a DLT occurs in 2/6 patients, then the preceding dose level will be considered the MTD.

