7.2.1.4 Transcutaneous Oxygen Pressure Assessment (TcPO₂₎

During the screening period the TcPO₂ will be measured at pre-defined locations on the anterior and posterior calf and dorsum of the foot. The limb/chest TcPO₂ index will be calculated by using the lesser of the lower limb measurements. Transcutaneous oxygen pressure methodology is instrument dependent and therefore the investigator will follow the standard procedures defined by their instrument's manufacturer and the written instructions provided by the Sponsor to standardize this procedure.

At multiple time points prior to and after treatment (Days 1, 15, 28, 59, 91, 180 and 365), the subject will have TcPO₂ measured at pre-defined locations on the anterior and posterior calf and dorsum of the foot. For analysis purposed, it is important that placement of the sensor used for the TcPO₂ measurement is always on the same pre-defined limb locations for screening and follow-up visits unless it is not possible (site amputated, areas of ulceration/gangrene). Marking the site with indelible ink is recommended. If a sensor placement site is unavailable due to amputation or areas of ulceration/gangrene, sensor placement site will be assigned a clinically equivalent default

TcPO₂ value of zero pressure ("0 mmHg"). Hard copy instrumentation printout will be included in the source documentation to support the TcPO₂ data.

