8.0 Adverse Events and Serious Adverse Events

8.1 Adverse Event Definition

An AE is the development of an undesirable medical condition or the deterioration of a pre-existing medical condition following or during exposure to a pharmaceutical product, whether or not considered causally related to the product. AEs will be graded according to the National Cancer Institute's Common Terminology for Adverse Events v3.0 criteria.

An undesirable medical condition can be symptoms (e.g., nausea, chest pain), signs (e.g., tachycardia, enlarged liver) or abnormal results of an investigation (e.g., laboratory findings, electrocardiogram).

Therefore, an AE would include the following:

- Any event that is new (i.e., was not seen prior to the start of the study).
- A condition detected or diagnosed after the trial medication administration, even though it may have been present prior to the start of the study.
- A pre-existing intermittent event or condition that recurs with increased intensity and/or frequency after the start of the study.
- A pre- or post-treatment event that results from study participation (i.e., invasive procedures, modification of subject's therapeutic regimen)
- A change in blood pressure or heart rate that results in discontinuation of dosage or that exceeds protocol-specified criteria

An AE does not include the following:

- The disease or disorder being studied, or a sign or symptom of that disease or disorder, unless it is more severe than expected for the subject's condition.
- An overdose of the study medication if the subject is asymptomatic.
- A medical or surgical procedure (e.g., surgery, endoscopy, tooth extraction).
 Depending on the trial design, such a procedure may be the result of an AE or may result in an AE, but is not an AE itself.
- A pre-existing condition or disease that does not worsen following study drug administration.
- Hospitalization for elective surgery for a pre-existing disease or condition that did not worsen or for cosmetic surgery.

In this study an AE can include an undesirable medical condition occurring at any time after screening procedures have been started until the final follow-up visit, even if no study treatment has been administered.

When an adverse event occurs, the Investigator must:

- 1. assess whether or not the test article caused the AE;
- 2. determine the intensity of the AE;
- 3. record the action taken regarding the test article;

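### On Day 15 the graded injection-site assessment comes only after the second injections, so Day 8 is the last scheduled graded reading before the re-dosing decision; SAP Table 23 also drops grade and visit from this primary endpoint.

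*Protocol*

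**What the plan says.** **Schedule.** Protocol 6.2.4 splits Day 15 into two lists. The list headed "Prior to the administration of the study agent, the following will be performed" has 14 entries, among them a physical examination and adverse events, but no injection-site assessment and no DLT item. The site assessment is in the list that follows drug administration. In Table 4-1 the row "Injection site reaction assessment" is marked at Day 1 post-dose and Day 8, blank at Day 15 pre-dose, and marked at Day 15 post-dose. SAP 10.9 likewise labels the Day 15 assessment post-dose. Protocol 4.1.1 lists Day 15 without saying which side of the dose it falls on; the other three places settle it.

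**DLT definition.** One of the three criteria in Protocol 7.1.9 is "Evidence for active tissue necrosis at the injection site within two weeks of study drug administration".

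**Hold on further dosing.** Protocol 6.2.2 suspends further dosing until DLT status is settled, or as the treating physician directs, if a subject has one of seven listed symptoms after discharge. The list includes fever, itching, a worsening leg ulcer, and redness or flushing at the site. It does not name necrosis.

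**Reporting.** Protocol 4.1.1 makes injection-site reaction a primary safety endpoint, graded 1 to 3 by CTCAE v3.0 at stated days. SAP 10.9 plans the number and percentage of subjects with a reaction, and the Table 23 shell has one yes/no row per cohort.

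**The concern.** The first-dose window for the necrosis criterion closes on about the day the second dose is due. A graded look at the first-dose sites is most useful just before the syringe is picked up again, because that is when it can change what happens to the subject. The plan schedules it just after, once 4 or 8 new injections have gone into the same leg, and 6.2.4 does not ask anyone to settle DLT status before proceeding. At stake is whether each subject's re-dosing decision rests on a structured, recorded reading or on the general examination and on what the subject reports.

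A second point concerns reporting. An endpoint defined by grade and day should be tabulated by grade and day. A single yes/no cannot separate a Grade 1 itch on Day 1 from a Grade 3 reaction on Day 21.

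**Working it through.** The plan gives no figure of its own here, so the check is a cross-reading of the schedule plus calendar arithmetic.

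**Inputs**
- First dose: Day 1.
- Day 8 visit: ±2 days, so Days 6 to 10 (Protocol 6.2.3).
- Second dose: Day 15 ±3 days, so Days 12 to 18 (Protocol 6.2.4).
- Necrosis window: two weeks after dosing (Protocol 7.1.9), so the first-dose window ends on Day 1 + 14 = Day 15.

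**Step 1: last graded reading to second dose** (day of dose 2 minus day of reading)
- Nominal: 15 − 8 = 7 days.
- Shortest: 12 − 10 = 2 days.
- Longest: 18 − 6 = 12 days.

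**Step 2: days of the first-dose necrosis window after the last pre-dose graded reading**

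| | Nominal | Range |
|---|---|---|
| As planned | 15 − 8 = 7 | 15 − 10 = 5 to 15 − 6 = 9 |
| With a reading on the day of dose 2 | 15 − 15 = 0 | 0 to 15 − 12 = 3 |

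When the second dose falls on Days 16 to 18, the window has already closed 1 to 3 days earlier, so the remainder is 0. These are calendar days that describe when information reaches the re-dosing decision. They are not probabilities.

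**Step 3: what the 14 pre-dose items are.** Physical examination, vital signs, ulcer photograph and measurement, pregnancy test, clinical laboratory tests, tumor markers, serum HGF, anti-HGF antibodies, TcPO2, hemodynamics, pain VAS, analgesic use, concomitant medications, adverse events. Graded site readings: 0. DLT checks: 0.

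**Step 4: can the grade stand in for the DLT check?** No. The injection-site row in Protocol 7.1.6 mentions necrosis only at Grade 3: "Ulceration or necrosis that is severe; operative intervention indicated". Protocol 7.1.9 counts any evidence of active necrosis at the site. A reaction below Grade 3 on that row does not by itself rule out a DLT.

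**Step 5: endpoint against output.** SAP 10.9 lists seven assessments (Day 1 post-dose, 8, 15 post-dose, 16, 21, 28, 59). Table 23 reduces them to one yes/no per subject. Listing 8, shared with MRA, is the only dedicated output that could carry visit and grade.

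**The case against.** The case on the other side is strong, and most of it stands.

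*The leg is examined before dose 2.* A full physical examination is due on Day 15, and Protocol 7.1.2.1 adds that "The lower extremities will be examined specifically for clinical evidence of CLI". TcPO2 is "measured at pre-defined locations on the anterior and posterior calf and dorsum of the foot", so staff are handling the calf. Adverse events are reviewed pre-dose and graded by CTCAE v3.0, and for each one the investigator must "record the action taken regarding the test article" (8.1). Appendix D requires new injections to be at least 2 cm from the old ones, so the injector must locate the old sites. The investigator may stop treatment for medical reasons at any time (6.6). Overt necrosis would probably be seen.

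*There is a DLT hold.* The 6.2.2 rule operates between the two doses and must be counted as cover. It is partial, because it depends on the subject reporting a listed symptom.

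A reader might draw three stronger conclusions that the documents do not support:

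- **That first- and second-dose reactions become inseparable.** The 2 cm rule, the leg diagram in the CRF and the recommended skin marking let a post-dose reader tell old sites from new. The documents do not show whether the form records reactions site by site, so a loss of attribution is not established.
- **That a DLT could escape the count or the safety committee, especially at the Cohort III to IV step.** Protocol 6.2.7 and 9.4 do let that review proceed once the other two subjects have had their second dose. But the post-dose reading is at the same visit and can cover the first-dose sites. Necrosis arising between Day 8 and Day 15 could still be found there, and the committee reviews all safety data. No route to a changed count or escalation decision is shown.
- **That a safety step present on Day 1 was left out of Day 15.** The Day 1 item, "Review all prior evaluations and confirm that subject meets all entry criteria", is an eligibility check. With no earlier dose, Day 1 had no DLT to check.

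On Table 23, SAP section 4 promises subject-level listings, and reactions also recorded as adverse events would appear by severity in Table 13. With about three subjects per cohort that softens the point. It does not give the primary endpoint a table that matches its definition.

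**Conclusion.** The point holds as a low-severity, inexpensive improvement. The last scheduled graded site reading precedes the re-dosing decision by 7 days nominally (2 to 12 across windows), and 6.2.4 has no explicit DLT check. The consequence is limited to the individual decision to give the second dose and to how cleanly the record before dose 2 is kept. The rate of missed reactions cannot be estimated from the documents. The reporting point is separate and does not depend on the timing: a primary safety endpoint defined by grade and day is summarized without either.

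This rests on three readings of the plan: that 6.2.4, Table 4-1 and SAP 10.9 govern the bare Day 15 in 4.1.1; that two weeks means 14 days counted from Day 1; and that no CRF page or site instruction outside these documents already requires a pre-dose site reading.

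**What to change.** 1. Add the existing graded injection-site assessment, applied to the first-dose sites, to the Day 15 pre-dose list in Table 4-1, Protocol 6.2.4 and SAP 10.9. Keep the post-dose reading. Beside it, add one line checking DLT status against 7.1.9, asked separately from the grade for the reason in Step 4.
2. Present SAP Table 23 by visit, with Day 15 pre-dose and post-dose shown separately, and by grade.

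A minor clerical correction can go in at the same time: SAP Table 11 puts the category for a dose withheld because of an earlier DLT under Day 1, where no earlier injection exists. It belongs in the Day 15 block, which now shows only yes and no.

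The cost is 12 to 15 extra copies of an existing form (one per planned subject), one check line at a visit that already includes a physical examination, and a longer Table 23. The ±3-day dosing window means the new reading will not always fall at the end of the DLT window: up to 3 window days remain if the second dose is given on Day 12.
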